3.0 PATIENT SELECTION

NOTE: PER NCI GUIDELINES, EXCEPTIONS TO ELIGIBILITY ARE NOT PERMITTED

3.1 Conditions for Patient Eligibility

3.1.1 Pathologically (histologically or cytologically) proven diagnosis of solid malignancy within 8 weeks of registration

NOTE: FDG-PET/CT scans are required for full staging of metastatic disease. If subject has had an FDG-PET/CT scan within the last 8 weeks, it will not need to be repeated.

NOTE: Pathological confirmation is not required for all disease sites as long as the sites of metastatic disease are radiographically and clinically consistent with metastatic disease from a known (biopsy proven) primary.

NOTE: the primary site does not have to be the site of pathological confirmation. For example, in a patient with a radiographic lung lesion with mediastinal

lymphadenopathy and a liver lesion, a liver biopsy which is constant with lung primary would preclude the necessity for further pathologic diagnosis.

3.1.2 Eligible disease sites include the following newly diagnosed disease types:

1. Breast
2. Prostate
3. GI (including colorectal, anal, esophagus, pancreas, gastric with the exception of colon cancer with resectable liver-only lesions)
4. Head and neck
5. Skin (melanoma and squamous cell carcinoma)
6. Lung (both small cell and non-small cell)
7. Sarcoma (both soft tissue and bone)
8. Gynecologic (endometrial, cervical, ovarian, vaginal, vulvar)

3.1.3 Patients are stage IV (M1) with any combination of T and N with oligometastatic disease as defined by 5 or fewer total sites of metastatic disease involving 3 or fewer organ systems

3.1.3.1 Examples of patients eligible for trial

- T3N2M1 NSCLC with 1 CNS metastatic lesion, 2 liver lesions, and 1 adrenal lesion.
- T4N1M1 colorectal cancer with 1 liver lesion, 4 bone lesions
- T3N0M1 gastric cancer with 1 supraclavicular lymph node, 2 liver lesions, and 2 CNS lesions

3.1.4 Metastatic disease sites must be treatable with SRS (at discretion of treating physician).

3.1.5 Primary disease site must be able to be treated with curative intent

3.1.6 Zubrod Performance Status 0-1

3.1.7 Age \geq 18

3.1.8 CBC/differential obtained within 4 weeks prior to registration on study, with adequate bone marrow function defined as follows:

3.1.8.1 Absolute neutrophil count (ANC) \geq 1,800 cells/mm³;

3.1.8.2 Platelets \geq 100,000 cells/mm³;

3.1.8.3 Hemoglobin \geq 8.0 g/dl (Note: The use of transfusion or other intervention to achieve Hgb \geq 8.0 g/dl is acceptable.);

3.1.9 Women of childbearing potential and male participants must practice adequate contraception

3.1.10 Patient must provide study specific informed consent prior to study entry.

3.2 Conditions for Patient Ineligibility

3.2.1 Ineligible disease sites include the following

- Lymphoma
- Leukemia
- Multiple myeloma
- Primary CNS
- Peritoneal carcinomatosis
- Colon cancer with resectable liver-only lesions

3.2.2 Examples of patients ineligible for trial

- T1N1M1 NSCLC with 1 CNS lesion, 1 bone lesion, 1 adrenal lesion and a cervical lymph node (4 sites of metastatic disease)
- T2N1M1 Gastric cancer with 6 liver lesions (more than 5 sites of metastatic disease)

3.2.3 Other

- Lung cancer with pleural effusion (wet IIIB) are not eligible
- Recurrent cancers are not eligible
- Diffuse metastatic spread confined to one organ system is ineligible; examples of this include leptomeningeal spread in the CNS and peritoneal carcinomatosis.

- 3.2.4 Prior systemic chemotherapy for the study cancer; note that prior chemotherapy for a different cancer is allowable but cannot have any other primary cancer diagnosed or treated within the last 3 years other than cutaneous skin cancers. Patient may have previous chemotherapy as treatment of this previous malignancy as long as the chemotherapy has completed more than 3 years ago.
- 3.2.5 Prior radiotherapy to the region of the study cancer that would result in overlap of radiation therapy fields
- 3.2.6 Severe, active co-morbidity, defined as follows:
 - 3.2.6.1 Unstable angina and/or congestive heart failure requiring hospitalization within the last 6 months;
 - 3.2.6.2 Transmural myocardial infarction within the last 6 months;
 - 3.2.6.3 Acute bacterial or fungal infection requiring intravenous antibiotics at the time of registration;
 - 3.2.6.4 Hepatic insufficiency resulting in clinical jaundice and/or coagulation defects; note, however, that laboratory tests for liver function and coagulation parameters are not required for entry into this protocol.
- 3.2.7 Pregnancy or women of childbearing potential and men who are sexually active and not willing/able to use medically acceptable forms of contraception; this exclusion is necessary because the treatment involved in this study may be significantly teratogenic.
- 3.2.8 **Oligometastatic disease sites not eligible based on concern for toxicity:**
 - * trachea involvement (direct invasion, tumors close to or abutting trachea are eligible)
 - * heart (direct invasion or involvement, pericardial lymph nodes can be treated)
- 3.2.9 Patients unable to have an FDG-PET/CT scan, either through insurance coverage, patient decision or other reason are not eligible for this study.
- 3.2.10 Patients unable to have SRS/SBRT through insurance coverage or ability to pay for SRS/SBRT

4.0 PRETREATMENT EVALUATIONS/MANAGEMENT

NOTE: This section lists baseline evaluations needed before the initiation of protocol treatment that do not affect eligibility.

4.1 The following are to be completed prior to treatment

- Complete history and physical
- Staging workup to determine oligometastatic disease, note that FDG-PET/CT scan is mandatory. Minimum metastatic workup is per NCCN guidelines for specific cancer type. If subject has had an FDG-PET/CT scan within the last 8 weeks, it will not need to be repeated.
- Measurements of metastatic disease sites (number of lesions and size of lesions, preferably volumetric data is available for better estimate of lesions).

4.2 The following will be ascertained at Study Registration:

- Name of institutional person registering this case

- Patient eligibility status
- Date the study-specific Consent Form was signed (must be signed prior to study entry)
- Patient's Initials (First Middle Last)
- Verifying Physician
- Patient's ID Number
- Date of Birth
- Race
- Ethnic Category (Hispanic or Latino; Not Hispanic or Latino; Unknown)
- Gender
- Treatment Start Date

5.0 TREATMENT OVERVIEW

- Treatment of metastatic disease: all sites of metastatic disease will be treated with SRS or SBRT (see section 6.0)
- Treatment of primary disease: primary disease will be treated using surgery, chemotherapy, radiation, or a combination of all three (see section 6.0, 7.0, 8.0). Treatment of the primary disease will be as per the UPMC pathway guidelines or NCCN guidelines individualized for the patient's stage and disease site with the exception that the patient will be considered M0 instead of M1. (For example, T3N3M1 NSCLC would be considered T3N3M0 and treated with definitive chemoradiotherapy).
- Sequence of therapy: SRS/SBRT will be used for all sites of metastatic disease in close approximation to initiation of treatment for the primary disease site (within 6 weeks). Ideally, SRS/SBRT would occur first followed by treatment to primary site. However, in some circumstances surgical resection of the primary site could precede SRS/SBRT, especially if surgical resection is required for pathological confirmation of disease. After completion of SRS/SBRT to the oligometastatic sites and treatment to the primary site, systemic chemotherapy can be given at the discretion of the medical oncologists (see Section 7.0).

6.0 RADIATION THERAPY

6.1 Non-radiosurgery radiation

External beam radiation (when indicated) would be initiated after completion of stereotactic radiosurgery. Details of radiation (IMRT or 3D, radiation energies, field sizes, doses, etc) is at the discretion of the treating radiation oncologist, encouragement will be given towards adherence to the UPMC Clinical Pathways specific to disease and patient characteristics. In some disease sites no radiation will be used after the completion of SRS/SBRT (for example, T2N0M1 lung cancer treated with SRS/SBRT to oligometastatic site then receiving surgical resection). Patients will be treated as if they are M0.

6.2 Stereotactic Radiosurgery (SRS) and Stereotactic Body Radiation Therapy (SBRT)

See Appendix IV for site-specific SRS/SBRT details. The following are general guidelines.

6.2.1 SRS/SBRT Timing: All SRS/SBRT treatments will be completed within 3 weeks (preferably 2 weeks).

6.2.2 Technical factors

SRS/SBRT has been formally defined and described in a published guideline from the American College of Radiology and American Society for Therapeutic Radiology and Oncology (47). This protocol will respect those guidelines. The term stereotactic for the purposes of this protocol implies the targeting, planning, and directing of therapy using beams of radiation along any trajectory in 3-D space toward a target of known 3-D coordinates. The coordinate system is defined by reliable “fiducial” markers. This differs from conventional radiation therapy, in which therapy is directed toward less-than-reliable skin marks or bony landmarks that are indirectly referenced to the tumor (surrogates). This protocol will require treatments to be conducted with the use of a fixed 3-D coordinate system defined by fiducials. The coordinate system defined by the fiducials should be directly related to the radiation-producing device (e.g., couch and gantry) in a reproducible and secure fashion. Capability should exist to define the position of targets within the patient according to this same 3-D coordinate system. As such, the patient is set up for each treatment with the intention of directing the radiation toward an isocenter or target according to the known 3-D coordinates as determined in the process of treatment planning. The nature of the fiducials themselves may include radiopaque markers or rods placed at known locations in a frame or fixed structure adjacent to the patient as well as use of the tumor itself as a fiducial (e.g., acquiring tomographic views of the tumor simultaneously with the treatment). Metallic “seeds” placed within the tumor will be allowed to constitute a fiducial so long as the methods are validated and a plan is in place to identify seed migration (e.g., redundant seeds placed). To allow fiducial stabilization and resolution of swelling, planning studies will be imaged 5-10 days after fiducial placement.

6.2.3 Patient Positioning

Patients will be positioned in a stable position capable of allowing accurate reproducibility of the target position from treatment to treatment. Positions uncomfortable for the patient should be avoided so as to prevent uncontrolled movement during treatments. A variety of immobilization systems may be used, including stereotactic frames that surround the patient on three sides and large rigid pillows (conforming to patients' external contours) with reference to the stereotactic coordinate system (see Section 6.1). Patient immobilization must be reliable enough to ensure that the gross tumor volume (GTV) does not deviate beyond the confines of the planning treatment volume (PTV) as defined in Section 6.2.4 with any significant probability (i.e., < 5%).

6.2.4 Localization

Isocenter or reference point port localization images (anterior/posterior and lateral) should be obtained at each treatment on the treatment unit or patients should undergo a tomographic imaging study immediately before treatment to ensure proper alignment of the geometric center (i.e., isocenter) of the simulated fields.

6.2.5 Treatment Planning/Target

Gross target volume (GTV) will be the tumor lesion defined by CT scan, FDG-PET scan and clinical information. Planning treatment volume (PTV) will be GTV with margin appropriate for set-up error and movement. There will be no elective nodal coverage.

6.2.6 Radiation doses and fractionation:

Dose and fractionation will be dependent on the lesion location and lesion size, the exact fractionation and dose is at the discretion of the treating physician. However, encouragement is made to adhere to the guidelines outlined in Appendix III. A minimum of 48 hours must be used in between SRS/SBRT treatments at each site. Note that patients can have SRS/SBRT everyday or multiple SRS/SBRT sessions in one day as long as the minimum time for each treatment site is met.

For example, if two lung lesions, adrenal, and liver sites were being treated, both lung sites could be treated Monday, Wednesday, and Friday, the liver on Tuesday, Thursday and the following Tuesday, and the adrenal on Monday, Wednesday, Friday of the second week.

EXAMPLE:

	Mon	Tues	Weds	Thurs	Fri
Wk 1	Lung #1 Lung #2	Liver	Lung #1 Lung #2	Liver	Lung #1 Lung #2
Wk 2	Adrenal	Liver	Adrenal		Adrenal

7.0 DRUG THERAPY

Chemotherapy

7.1 Chemotherapy guidelines for primary disease

Chemotherapy (when indicated) would be initiated after completion of stereotactic radiosurgery. Chemotherapy choice of agents is at the discretion of the treating medical oncologist, encouragement will be given towards adherence to the UPMC Clinical Pathways specific to disease and patient characteristics. In some disease sites no chemotherapy will be used.

7.2 Chemotherapy guidelines after treatment for metastatic disease

At the discretion of the medical oncologist, chemotherapy may be initiated after treatment of the primary disease site has been completed in accordance with UPMC Clinical Pathways or NCCN guidelines for treatment of M1 disease for the patient's primary disease site.

For example; T1N0M1 NSCLC with solitary adrenal lesion is treated with SBRT to the adrenal lesion followed by lobectomy (treatment option for T1N0M0 NSCLC). After surgical resection, medical oncologists could choose to place patient on systemic chemotherapy that would be indicated for patient with M1 NSCLC).

8.0 SURGERY

8.1 Surgery guidelines

Surgery (when indicated) would be initiated after completion of stereotactic radiosurgery. Type of surgical operation is at the discretion of the treating surgeon, encouragement will be given towards adherence to the UPMC pathways specific to disease and patient characteristics. In some disease sites no surgery will be used.

9.0 OTHER THERAPY

9.1 Permitted Supportive Therapy

All supportive therapy for optimal medical care will be given during the study period at the discretion of the attending physician(s) within the parameters of the protocol and documented on each site's source documents as concomitant medication. [Include the following sections as appropriate]

- 9.1.1 Anticonvulsants
- 9.1.2 Antiemetics
- 9.1.3 Anticoagulants
- 9.1.4 Antidiarrheals
- 9.1.5 Analgesics

- 9.1.6 Hematopoietic Growth Factors
- 9.1.7 Herbal products
- 9.1.8 Nutritional supplementation

10.0 PATIENT ASSESSMENTS

10.1 Study Parameters: See Appendix I.

10.2 Evaluation during Study

10.2.1 If clinically indicated, blood counts and other labs should be obtained during therapy.

10.2.2 Toxicity will be evaluated during the study using Common Cancer Toxicity Criteria V 4.0

10.3 Evaluation after study

10.3.1 Patients will be seen in follow-up with study physicians 6 weeks after completion of SRS/SBRT and then at 3 month intervals for 3 years and 6 months thereafter.

10.3.2 QOL survey to be performed prior to therapy, after SRS/SBRT and at subsequent follow-up visits using the FACT-G survey. See Appendix IV.

10.3.3 Toxicity will be evaluated after the study using Common Cancer Toxicity Criteria V 4.0

10.3.4 Follow-up imaging should be performed at least every 3 months for the first two years from completion of therapy and every 6 months afterwards until five years from the completion of therapy. FDG-PET/CT scan for follow-up is recommended but not required.

10.3.5 Measurement of Response for CT scans

Response will be evaluated in this study using the international criteria proposed by the Response Evaluation Criteria in Solid Tumors (RECIST) Committee [JNCI 92(3): 205-216, 2000] See <http://ctep.info.nih.gov/guidelines/recist.html> for further details.

1. Measurable disease - the presence of at least one measurable lesion; if the measurable disease is restricted to a solitary lesion, its neoplastic nature should be confirmed by cytology/histology.
2. Measurable lesions - lesions that can be accurately measured in at least one dimension with longest diameter \geq 20 mm using conventional techniques or \geq 10 mm with spiral CT scan.
3. Non-measurable lesions - all other lesions, including small lesions (longest diameter $<$ 20 mm with conventional techniques or $<$ 10 mm with spiral CT scan), i.e., bone lesions, leptomeningeal disease, ascites, pleural/pericardial effusion, inflammatory breast disease, lymphangitis cutis/pulmonis, cystic lesions, and also abdominal masses that are not confirmed and followed by imaging techniques

Response Criteria: Evaluation of target lesions

*Complete Response (CR): Disappearance of all target lesions

*Partial Response (PR): At least a 30% decrease in the sum of the LD of target lesions, taking as reference the baseline sum LD

*Progressive Disease (PD): At least a 20% increase in the sum of the LD of target lesions, taking as reference the smallest sum LD recorded since the treatment started or the appearance of one or more new lesions

*Stable Disease (SD): Neither sufficient shrinkage to qualify for PR nor sufficient increase to qualify for PD, taking as reference the smallest sum LD since the treatment started

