The outcomes of patients treated with SBRT for multiple organ metastases have also been reported. The University of Rochester reported an analysis on 121 patients with 1-5 metastases treated on two consecutive protocols. Patients on both protocols could have had previous therapy for their disease; only 27 patients had oligometastatic disease at initial presentation. The first protocol treated breast cancer patients with limited metastases, in which no brain lesions were treated. The second protocol included patients with cancer from any primary site and limited metastases including a brain primary. After treatment with ten fractions of 5 Gy over 2 weeks (10 fractions), metastatic lesions were controlled 77% of the time at 2 years (25). Milano (5) reported prospective data on breast cancer patients with oligometastatic disease (less than 5 sites) comparing patients treated with SBRT to those receiving only palliative therapy. Four-year survival was significantly improved in SBRT patients (59% versus 0%). University of Chicago (53) reported on a prospective trial in 29 oligometastatic patients (one to five sites and a life expectancy > 3 months, 81% had prior systemic treatment) who had 56 metastatic lesions treated with SBRT (3 fractions ranging from a total dose of 24 to 36 Gy). The authors found a control rate of 56% for treated sites and only 2 patients had grade 3 or higher toxicity.

From the data available, patients with oligometastatic disease appear to benefit in terms of disease control from SBRT. At this point, no one is able to adequately predict which patients have favorable oligometastatic disease and are good candidates for aggressive and potentially curative therapy and which patients are destined to have development of widespread metastatic disease. Some proposed factors for patients likely to proceed to widespread metastatic disease include size and grade of primary tumor, site of oligometastatic disease, and lymph node status. In order to best treat patients, it is important that careful studies be performed to collect clinical information on patients with oligometastatic disease to analyze patient subsets most likely to benefit from treatment.

While disease outcome is certainly an important endpoint, quality of life (QOL) also is of significant importance, especially in patients with metastatic disease that have traditionally thought to

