2.0 OBJECTIVES

Primary objective: Delivery of SBRT to multiple sites in a safe and effective manner with acceptable toxicity

Primary Endpoints:

- Presence of multiple sites (between 2 and 5 sites)
- Acceptable toxicity: Grade 3 or less

Secondary Objectives/Endpoints:

- Quality of life (as measured by the FACT quality of life surveys, see appendix IV)
- Local control of metastatic sites (with measurable/quantitative assessment): proportion of patients with Complete Response (CR), Partial Response (PR), or Stable Disease (SD)
- Local control of primary site (with measurable/quantitative assessment): proportion of patients with local Complete Response (CR), Partial Response (PR), or Stable Disease (SD)
- Overall survival (OS)
- Two-year Overall Survival
- Analysis of patterns of failure post-SRS/SBRT (subsequent sites of failure and time to failure): proportion of patients with Progressive Disease (PD)

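### With CT follow-up and two or more measurable metastases, local control is read from a summed diameter, so growth of one SBRT-treated lesion can be counted as controlled

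*Combined protocol and SAP*

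**What the plan says.** Section 2.0 (repeated in the Summary) lists as a secondary endpoint "Local control of metastatic sites (with measurable/quantitative assessment): proportion of patients with Complete Response (CR), Partial Response (PR), or Stable Disease (SD"). The unit is the patient. Local control of the primary is a separate endpoint in the same list.

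For CT, section 10.3.5 builds the response categories on the target lesions taken together. CR requires all of them to disappear. PR is "At least a 30% decrease in the sum of the LD of target lesions, taking as reference the baseline sum LD". PD is "At least a 20% increase in the sum of the LD of target lesions", measured from the lowest sum seen since treatment began, or any new lesion. SD is whatever is neither PR nor PD.

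Section 5.0 states that "all sites of metastatic disease will be treated with SRS or SBRT", and eligibility allows up to five metastatic sites. For FDG-PET, section 10.3.6 uses visual criteria with no sum. Section 10.3.4 recommends follow-up PET/CT but does not require it. Section 10.4 assigns CT or PET criteria according to the follow-up scan, but only for stopping protocol treatment. Section 11.3 contains no analysis of local control.

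**The concern.** Local control asks whether each irradiated site has failed. Every metastasis here receives its own ablative treatment, so a failure at one site is a failure whatever the others do. A single sum over all target lesions cannot show that. One growing lesion may be too small a share of the total to move it by 20%, or its growth may be cancelled by shrinkage elsewhere.

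The patients most exposed are those with several lesions, and the primary endpoint in section 2.0 is framed around patients with 2 to 5 sites. Section 11.2 names local control among the three outcomes for which each cancer-type subset needs a reasonable estimate. If the chance of missing a failed lesion depends on how many lesions a patient has, subsets that present with different lesion counts are not measured on the same scale.

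**Working it through.** The plan gives no target rate, test or worked figure for local control, so there is nothing to reproduce first. The sample size in 11.2 (40 × 1.10 = 44) does not enter this point.

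**Rule applied (10.3.5).** S is the current sum. PD if S ≥ 1.2 × nadir; otherwise PR if S ≤ 0.7 × baseline; otherwise SD. No new lesions appear in any case below.

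**Assumption.** The documents give no lesion sizes. All k metastases are taken as measurable and 20 mm at baseline, so the baseline sum is 20k mm.

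**A. Shrinkage is recorded first, growth comes later (dilution).** All but one lesion shrink 30% to 14 mm, and the remaining lesion is unchanged. Nadir N = 20 + 14(k − 1). Later growth of d mm in that lesion escapes PD while d < 0.2N.

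| k | N (mm) | PD at (mm) | Growth not scored as PD |
|---|---|---|---|
| 2 | 34 | 40.8 | below 6.8 mm (34%) |
| 3 | 48 | 57.6 | below 9.6 mm (48%) |
| 4 | 62 | 74.4 | below 12.4 mm (62%) |
| 5 | 76 | 91.2 | below 15.2 mm (76%) |

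- k = 5, lesion grows from 20 to 35 mm (+75%): 4 × 14 + 35 = 91 < 91.2, and 91 > 70, so SD.
- k = 3, lesion grows from 20 to 29 mm (+45%): 2 × 14 + 29 = 57 < 57.6, and 57 > 42, so SD.

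**B. Shrinkage and growth first appear on the same scan (offset).** One lesion doubles to 40 mm and the others shrink by a fraction x. S = 40 + 20(k − 1)(1 − x), and the nadir is still the baseline sum 20k. PD is avoided when x > (1 − 0.2k)/(k − 1), that is, above 60%, 20%, 6.7% and 0% for k = 2, 3, 4 and 5.

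With x = 30%:
- k = 2: 54/40 = +35%, PD
- k = 3: 68/60 = +13%, SD
- k = 4: 82/80 = +2.5%, SD
- k = 5: 96/100 = −4%, SD

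With x = 80% and k = 5, S = 56 (−44%), which is PR although one lesion has doubled.

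**C. Nadir applied while the others keep shrinking.** Four lesions. First scan: 20 + 3 × 14 = 62. Next scan: 40 + 3 × 8 = 64. 64/62 = +3.2% from nadir and 64/80 = −20% from baseline, so SD with a doubled lesion.

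**D. The same 20% threshold applied lesion by lesion.** The growing lesion in every example above (+45% to +100%) would be a local failure.

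**The case against.** **The nadir rule and 3-monthly imaging catch much of this.** That is partly right. If four of five 20 mm lesions first fall to 10 mm, the nadir is 60 mm. Later growth of the fifth from 20 to 50 mm gives 90 mm (+50%), which is PD. Deep early shrinkage followed by large growth will be caught. Cases A and C show that the nadir rule narrows the masking without removing it.

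**PET-followed patients are not scored on a sum.** This stands, and the point is limited to CT follow-up accordingly. The PET route does not settle the matter, because follow-up PET is optional and no section says which route governs local control. Section 10.3.6 also has no rule for mixed response: one lesion brighter and four dimmer fits the wording of both PR and PD.

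**A reader might infer that resecting the primary lowers the sum and hides growing metastases.** The documents do not support this. Primary control is its own endpoint, and nothing puts the primary's diameter into the metastatic-site score. Nothing expressly excludes it either, so one clarifying sentence is worth adding. Even with the primary included, masking would need resection and growth to appear first on the same scan.

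**A reader might infer that control falls mechanically with lesion count**, for example from 0.77² = 59% to 0.77⁵ = 27% under independence. Those figures describe an endpoint requiring every lesion to be controlled. Under the summed rule the effect runs the other way, because more lesions make a failure easier to miss.

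**A reader might infer that the introduction's benchmarks are all per lesion.** They are mixed. Section 1.0 cites 77% of lesions and 56% of treated sites, but also 42 of 49 evaluable patients controlled and 90% of patients free of local failure. The plan proposes no formal comparison with any of them.

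**It is a secondary endpoint, and patterns of failure are analysed as well.** Both are true, and they limit the importance. The patterns-of-failure endpoint recovers some site information, although its stated proportion is again of patients with PD.

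**Conclusion.** The concern holds for patients followed by CT with two or more measurable metastases. Following the plan as written, a treated lesion that has clearly grown can be reported as controlled. If equal 20 mm lesions otherwise shrink 30% first, growth of just under 34%, 48%, 62% and 76% of the failing lesion's own size goes unscored with 2, 3, 4 and 5 lesions. If the changes coincide on one scan, a full doubling is SD with three or more lesions. These sizes are illustrative. The number of patients affected cannot be calculated from the documents.

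It would be tempting to conclude that the reported rate must be too high. Summing does push it up, but the new-lesion clause in PD counts failures outside the treated sites and pushes it down, so the net direction is uncertain. What is established is that the endpoint does not measure control of the treated sites, and that its error depends on lesion count. This should be corrected, but it does not affect the sample size or the primary endpoint.

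**What to change.** In sections 2.0 and 10.3.5:

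- Score local control separately for each SBRT-treated lesion. Define local failure as an increase of at least 20% in that lesion's own longest diameter from its own nadir, with a minimum absolute increase set by the sponsor. Without that minimum, 2 mm on a 10 mm lesion would count as failure.
- For non-measurable lesions (10.3.5 places bone lesions here) and PET-assessed lesions, apply the visual criteria of 10.3.6, or a stated in-field progression call, lesion by lesion. State which route governs this endpoint.
- Report the per-lesion control rate with allowance for clustering within patient, and the proportion of patients with every treated lesion controlled.
- State that the primary is scored separately and does not enter the metastatic-site score.
- Keep summed RECIST for overall response.

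The cost is small. Section 4.1 already requires "Measurements of metastatic disease sites (number of lesions and size of lesions") at baseline, and individual diameters must be measured to form the sum. The change adds a few lines to the response form and no scans. The reported control rate may be less favourable.
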